### 6.3.2 DISEASE PARAMETERS

Measurable disease: Measurable lesions are defined as those that can be accurately measured in at least one dimension (longest diameter to be recorded) as  $\geq 20$  mm by chest x-ray, as  $\geq 10$  mm with CT scan, or  $\geq 10$  mm with calipers by clinical exam. All tumor measurements must be recorded in millimeters (or decimal fractions of centimeters). The same criteria will be applied to measurements from MRI.

Malignant lymph nodes. To be considered pathologically enlarged and measurable, a lymph node must be  $\geq 15$  mm in short axis when assessed by CT scan (CT scan slice thickness recommended to be no greater than 5 mm). At baseline and in follow-up, only the short axis will be measured and followed. The same criteria will be applied to measurements from MRI.

Non-measurable disease. All other lesions (or sites of disease), including small lesions (longest diameter  $< 10$  mm or pathological lymph nodes with  $\geq 10$  to  $< 15$  mm short axis), are considered non-measurable disease. Bone lesions, leptomeningeal disease, ascites, pleural/pericardial effusions, lymphangitis cutis/pulmonitis, inflammatory breast disease, and abdominal masses (not followed by CT or MRI), are considered as non-measurable.

Note: Cystic lesions that meet the criteria for radiographically defined simple cysts should not be considered as malignant lesions (neither measurable nor non-measurable) since they are, by definition, simple cysts.

‘Cystic lesions’ thought to represent cystic metastases can be considered as measurable lesions, if they meet the definition of measurability described above. However, if non-cystic lesions are present in the same patient, these are preferred for selection as target lesions.

Target lesions. All measurable lesions up to a maximum of 2 lesions per organ and 5 lesions in total, representative of all involved organs, should be identified as **target lesions** and recorded and measured at baseline. Target lesions should be selected on the basis of their size (lesions with the longest diameter), be representative of all involved organs, but in addition should be those that lend themselves to reproducible repeated measurements. It may be the case that, on occasion, the largest lesion does not lend itself to reproducible measurement in which circumstance the next largest lesion, which can be measured reproducibly should be selected. A sum of the diameters (longest for non-nodal lesions, short axis for nodal lesions) for all target lesions will be calculated and reported as the baseline sum diameters. If lymph nodes are to be included in the sum, then only the short axis is added into the sum. The baseline sum diameters will be used as reference to further characterize any objective tumor regression in the measurable dimension of the disease.

Non-target lesions. All other lesions (or sites of disease) including any measurable lesions over and above the 5 target lesions should be identified as **non-target lesions** and should also be recorded at baseline. Measurements of these lesions are not required, but the presence, absence, or in rare cases unequivocal progression of each should be noted throughout follow-up.

### 6.3.3 METHODS FOR EVALUATION OF MEASURABLE DISEASE

All measurements should be taken and recorded in metric notation using a ruler or calipers. All baseline evaluations should be performed as closely as possible to the beginning of treatment and never more than 4 weeks before the beginning of the treatment.

The same method of assessment and the same technique should be used to characterize each identified and reported lesion at baseline and during follow-up. Imaging-based evaluation is

preferred to evaluation by clinical examination unless the lesion(s) being followed cannot be imaged but are assessable by clinical exam.

Clinical lesions: Clinical lesions will only be considered measurable when they are superficial (e.g., skin nodules and palpable lymph nodes) and  $\geq 10$  mm diameter as assessed using calipers (e.g., skin nodules). In the case of skin lesions, documentation by color photography, including a ruler to estimate the size of the lesion, is recommended.

Chest x-ray: Lesions on chest x-ray are acceptable as measurable lesions when they are clearly defined and surrounded by aerated lung. However, CT is preferable.

Conventional CT and MRI: This guideline has defined measurability of lesions on CT scan based on the assumption that CT slice thickness is 5 mm or less. If CT scans have slice thickness greater than 5 mm, the minimum size for a measurable lesion should be twice the slice thickness. MRI is also acceptable in certain situations (e.g. for body scans).

Use of MRI remains a complex issue. MRI has excellent contrast, spatial, and temporal resolution; however, there are many image acquisition variables involved in MRI, which greatly impact image quality, lesion conspicuity, and measurement. Furthermore, the availability of MRI is variable globally. As with CT, if an MRI is performed, the technical specifications of the scanning sequences used should be optimized for the evaluation of the type and site of disease. Furthermore, as with CT, the modality used at follow-up should be the same as was used at baseline and the lesions should be measured/assessed on the same pulse sequence. It is beyond the scope of the RECIST guidelines to prescribe specific MRI pulse sequence parameters for all scanners, body parts, and diseases. Ideally, the same type of scanner should be used and the image acquisition protocol should be followed as closely as possible to prior scans. Body scans should be performed with breath-hold scanning techniques, if possible.

PET-CT: At present, the low dose or attenuation correction CT portion of a combined PET-CT is not always of optimal diagnostic CT quality for use with RECIST measurements. However, if the site can document that the CT performed as part of a PET-CT is of identical diagnostic quality to a diagnostic CT (with IV and oral contrast), then the CT portion of the PET-CT can be used for RECIST measurements and can be used interchangeably with conventional CT in accurately measuring cancer lesions over time. Note, however, that the PET portion of the CT introduces additional data, which may bias an investigator if it is not routinely or serially performed.

Ultrasound: Ultrasound is not useful in assessment of lesion size and should not be used as a method of measurement. Ultrasound examinations cannot be reproduced in their entirety for independent review at a later date and, because they are operator dependent, it cannot be guaranteed that the same technique and measurements will be taken from one assessment to the next. If new lesions are identified by ultrasound in the course of the study, confirmation by CT or MRI is advised. If there is concern about radiation exposure at CT, MRI may be used instead of CT in selected instances.

Endoscopy, Laparoscopy: The utilization of these techniques for objective tumor evaluation is not advised. However, such techniques may be useful to confirm complete pathological response when biopsies are obtained or to determine relapse in trials where recurrence following complete response (CR) or surgical resection is an endpoint.

Tumor markers: Tumor markers alone cannot be used to assess response. If markers are initially above the upper normal limit, they must normalize for a patient to be considered in complete

clinical response. Specific guidelines for both CA-125 response (in recurrent ovarian cancer) and PSA response (in recurrent prostate cancer) have been published (45-47). In addition, the Gynecologic Cancer Intergroup has developed CA-125 progression criteria, which are to be integrated with objective tumor assessment for use in first-line trials in ovarian cancer(48).

Cytology, Histology: These techniques can be used to differentiate between partial responses (PR) and complete responses (CR) in rare cases (e.g., residual lesions in tumor types, such as germ cell tumors, where known residual benign tumors can remain).

The cytological confirmation of the neoplastic origin of any effusion that appears or worsens during treatment when the measurable tumor has met criteria for response or stable disease is mandatory to differentiate between response or stable disease (an effusion may be a side effect of the treatment) and progressive disease.

FDG-PET: While FDG-PET response assessments need additional study, it is sometimes reasonable to incorporate the use of FDG-PET scanning to complement CT scanning in assessment of progression (particularly possible 'new' disease). In this study, we will explore the utility of FDG-PET in the management of patients with wt-GIST. New lesions on the basis of FDG-PET imaging can be identified according to the following algorithm:

- a. Negative FDG-PET at baseline, with a positive FDG-PET at follow-up is a sign of PD based on a new lesion.
- b. No FDG-PET at baseline and a positive FDG-PET at follow-up: If the positive FDG-PET at follow-up corresponds to a new site of disease confirmed by CT, this is PD. If the positive FDG-PET at follow-up is not confirmed as a new site of disease on CT, additional follow-up CT scans are needed to determine if there is truly progression occurring at that site (if so, the date of PD will be the date of the initial abnormal FDG-PET scan). If the positive FDG-PET at follow-up corresponds to a pre-existing site of disease on CT that is not progressing on the basis of the anatomic images, this is not PD.
- c. FDG-PET may be used to upgrade a response to a CR in a manner similar to a biopsy in cases where a residual radiographic abnormality is thought to represent fibrosis or scarring. The use of FDG-PET in this circumstance should be prospectively described in the protocol and supported by disease-specific medical literature for the indication. However, it must be acknowledged that both approaches may lead to false positive CR due to limitations of FDG-PET and biopsy resolution/sensitivity.

Note: A 'positive' FDG-PET scan lesion means one which is FDG avid with an uptake greater than twice that of the surrounding tissue on the attenuation corrected image.

#### 6.3.4 RESPONSE CRITERIA

##### 6.3.4.1 Evaluation of Target Lesions

Complete Response (CR): Disappearance of all target lesions. Any pathological lymph nodes (whether target or non-target) must have reduction in short axis to <10 mm.

Partial Response (PR): At least a 30% decrease in the sum of the diameters of target lesions, taking as reference the baseline sum diameters.

Progressive Disease (PD): At least a 20% increase in the sum of the diameters of target lesions, taking as reference the smallest sum on study (this includes the baseline sum if that is the smallest

on study). In addition to the relative increase of 20%, the sum must also demonstrate an absolute increase of at least 5 mm. (Note: the appearance of one or more new lesions is also considered progressions).

**Stable Disease (SD):** Neither sufficient shrinkage to qualify for PR nor sufficient increase to qualify for PD, taking as reference the smallest sum diameters while on study.

#### 6.3.4.2 Evaluation of Non-Target Lesions

**Complete Response (CR):** Disappearance of all non-target lesions and normalization of tumor marker level. All lymph nodes must be non-pathological in size (<10 mm short axis).

Note: If tumor markers are initially above the upper normal limit, they must normalize for a patient to be considered in complete clinical response.

**Non-CR/Non-PD:** Persistence of one or more non-target lesion(s) and/or maintenance of tumor marker level above the normal limits.

**Progressive Disease (PD):** Appearance of one or more new lesions and/or *unequivocal progression* of existing non-target lesions. *Unequivocal progression* should not normally trump target lesion status. It must be representative of overall disease status change, not a single lesion increase.

Although a clear progression of “non-target” lesions only is exceptional, the opinion of the treating physician should prevail in such circumstances, and the progression status should be confirmed at a later time by the review panel (or Principal Investigator).

#### 6.3.4.3 Evaluation of Best Overall Response

The best overall response is the best response recorded from the start of the treatment until disease progression/recurrence (taking as reference for progressive disease the smallest measurements recorded since the treatment started). The patient's best response assignment will depend on the achievement of both measurement and confirmation criteria.

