### 3.6.1 CRITERIA FOR REMOVAL FROM PROTOCOL THERAPY

Subjects will be removed from study therapy and followed until off-study criteria are met for any one of the following:

- Unacceptable toxicity (treatment limiting toxicity after two dose reductions, or treatment-limiting toxicity does not resolve to grade  $\leq$ 1 or baseline in  $\leq$  6 weeks of a drug free period). Patients who are removed from therapy for unacceptable toxicity will continue to undergo disease evaluations as per [Appendix 9](#) until they develop progressive disease.

- Concurrent use of agents that prolong the QTc: Vandetanib use must be discontinued if one of the QTc prolonging agents in Group 1 of [Appendix 7](#) is started.
- Progressive disease; clinical or radiographic evidence of progressive disease will discontinue vandetanib (see [Section 6.3](#)). If possible, tumor progression should be documented radiographically.
- Participant requests to be withdrawn from active therapy
- Positive pregnancy test
- Investigator discretion, which may include
  - The development of a concurrent serious medical condition that might preclude or contraindicate the further administration of vandetanib.
  - It is deemed in the best interest of the patient, and the reasons for discontinuation of vandetanib should be noted in the patient's medical record.
  - Serious protocol violation, such as non-compliance, as determined by the Principal Investigator.
- Death

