## **4 CONCOMITANT MEDICATIONS/MEASURES**

At screening, all prior anti-cancer therapy and administration of all other concomitant medication in use on the day of enrollment (signature of the ICF) will be recorded. All concomitant medications that the patient has been taking since the time of the last visit, medications the patient started between visits and all new medications will be recorded at each visit until the completion of the final analysis. If a patient discontinues vandetanib before the final analysis, all medications including any medications started within the 60 days after the last dose of vandetanib, will be recorded at the appropriate discontinuation visit and the 60-day follow-up visit.

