#### **4.1.1 TREATMENT FOR CANCER**

Prior to starting treatment (according to [Section 2.1](#)) and while the patient remains on study treatment, patients must not be given any concurrent cancer therapy, including cytotoxic agents, radiotherapy, biological response modifiers (including cytokines), hormonal therapy (used specifically for cancer treatment), or any other investigational agents.

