### 6.3.6 PROGRESSION-FREE SURVIVAL

Progression-free survival (PFS) is defined as the duration of time from start of treatment to time of progression or death, whichever occurs first.

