## **8 STATISTICAL SECTION**

### **8.1 PRIMARY ENDPOINT**

The study will be conducted as a small, optimal two-stage phase II trial(49), in order to rule out an unacceptably low 5% overall response rate (ORR;  $p_0=0.05$ ), in favor of a slightly higher response rate of 25% ( $p_1=0.25$ ). With  $\alpha=0.10$  (probability of accepting a poor treatment=0.10) and  $\beta = 0.10$  (probability of rejecting a good treatment=0.10), the study will initially enroll 9 evaluable patients and if 0 of the 9 have a response, then no further patients will be accrued. If 1 or more the first 9 (11.1% or more) have a response, then accrual would continue until a total of 24 patients have enrolled. Only complete responses (CR) and partial responses (PR) will be counted towards the overall response rate. As it may take several weeks to months to determine if a patient has experienced a response, a temporary pause in the accrual to the trial may be necessary to ensure that enrollment to the second stage is warranted. If there are 1 to 2 responses in 24 patients, this would be an uninterestingly low response rate, while if there were 3 or more responses in 24 (12.5% or more) patients, then this would be sufficiently interesting to warrant further study in later trials. Under the null hypothesis (5% response rate), the probability of early termination is 63%.

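### The best-response window does not end at the next anticancer treatment, so a response to later therapy or tumour resection could be counted for vandetanib

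*Combined protocol and SAP*

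**What the plan says.** The primary endpoint is the count of complete and partial responses (section 8.1). The design is a two-stage one, set up "in order to rule out an unacceptably low 5% overall response rate" "in favor of a slightly higher response rate of 25" per cent. It stops if none of the first 9 evaluable patients responds, and it calls 3 or more responses in 24 interesting.

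Four other sections decide which scans can contribute a response:

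- **6.3.4.3 (window):** "The best overall response is the best response recorded from the start of the treatment until disease progression/recurrence". Measurement and confirmation criteria must also be met, with confirmation at 4 weeks or more (6.3 and the table in 6.3.4.3).
- **4.1.1 (other therapy):** "while the patient remains on study treatment, patients must not be given any concurrent cancer therapy". The treatments named there are cytotoxic agents, radiotherapy, biological response modifiers, hormonal therapy and investigational agents. Surgery is not named, and nothing is said about the period after treatment stops.
- **3.6.1 (scanning after stopping):** "Patients who are removed from therapy for unacceptable toxicity will continue to undergo disease evaluations as per" Appendix 9, until they progress.
- **3.3.3 (surgery):** patients needing elective surgery have vandetanib held, are restaged, and resume. Tumour surgery is not excluded.

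Starting another anticancer treatment is not an off-study criterion (3.6.2). The statistical section has no cut-off rule for response.

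**The concern.** Each rule is reasonable alone. Together they leave a gap in attribution.

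Take a patient who stops vandetanib for toxicity with stable disease. The patient remains evaluable under 6.3.1 after one cycle and one re-evaluation. Scans continue, other therapy is no longer barred, and the response window is still open. If a later agent produces a 30% decrease confirmed at 4 weeks, the written rules make this patient a partial responder to vandetanib. Confirmation does not protect against this, because a response to the later agent can be confirmed too.

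The second route is surgical and does not require the patient to leave treatment. If a target lesion is resected and the patient is restaged and resumes, the sum of diameters can fall for reasons unrelated to the drug. The response criteria do not say how a resected target lesion is handled. The protocol expects surgery for tumour-related symptoms in this disease (1.2.1), and it plans to collect tissue from clinically indicated operations (5.1.2, 5.1.4).

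What is at stake is a decision rule that turns on single responses: 0 against 1 at stage 1, and 2 against 3 at the end.

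**Working it through.** **Inputs from section 8.1.** Null rate 0.05, target rate 0.25, first stage 9 patients, total 24. Stop at 0 of 9; call the result interesting at 3 or more of 24. Alpha is defined as "probability of accepting a poor treatment=0.10", beta is also 0.10, and the stated early-termination probability under the null is 63%.

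**Formula.** Let p be the rate at which patients are *counted* as responders. X is the number counted in the first 9 and Y the number in the next 15.

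- Early termination: P(X=0) = (1−p)^9
- Declaring activity: P(X=1)·P(Y≥2) + P(X=2)·P(Y≥1) + P(X≥3)

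**Step 1: reproduce the plan at p = 0.05.** P(X=0) = 0.95^9 = 0.630, which matches the stated 63%. The other terms are P(X=1) = 0.2985, P(X=2) = 0.0629, P(X≥3) = 0.0084, P(Y≥2) = 0.1710 and P(Y≥1) = 0.5367. Declaring activity: 0.2985×0.1710 + 0.0629×0.5367 + 0.0084 = 0.093. At p = 0.25 the same formula gives 0.903. The design meets its stated error rates, and an exhaustive search returns 0/9, 2/24 as the optimal design. Nothing is wrong with the design arithmetic.

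**Step 2: add credited responses from later treatment.** The documents do not give a contamination rate, so these are assumptions. If a share f of patients start other therapy before progression while still being scanned, and a share q of those respond, the counted rate at a true 5% is p = 0.05 + 0.95·f·q. The last row instead assumes directly that a further 2% of all patients gain a credited response.

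| Assumption | Counted rate | Early termination | Declares activity |
|---|---|---|---|
| None | 0.0500 | 0.630 | 0.093 |
| f = 5%, q = 10% | 0.05 + 0.95×0.05×0.10 = 0.0548 | 0.602 | 0.114 |
| 10% stop for toxicity, half of them switch (f = 5%), q = 15% | 0.05 + 0.95×0.05×0.15 = 0.0571 | 0.589 | 0.125 |
| 2% of all patients gain a credited response | 0.05 + 0.02 = 0.0700 | 0.520 | 0.191 |

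Each contaminated case is above the planned 0.10, the mildest only slightly.

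**Step 3: the stage that was reached.** Section 8.3 records nine patients enrolled before closure to accrual. One misattributed response moves the result from 0/9 (0%, exact 95% CI 0 to 34%) to 1/9 (11%, exact 95% CI 0.3 to 48%), and the stage 1 rule from stop to continue.

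**The case against.** The strongest reply is that the route is narrow. Continued scanning after stopping is explicit only for removal for unacceptable toxicity. Other patients have an off-treatment visit with no imaging in its list (3.5.3.1), an end-of-therapy column in Appendix 9, and contact at least annually. A false responder through later therapy must meet the toxicity rule, be free of progression, start another treatment before progressing, shrink by 30% and have it confirmed. This stands. It is why the effect should be described as possible and probably small. It does not close the gap, and the surgical route is separate from it.

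Three stronger readings are tempting, and the documents do not support them.

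- **That later therapy would go unseen because medication recording ends at the 60-day visit.** Section 4 says that, for patients who stop early, "all medications including any medications started within the 60 days after the last dose of vandetanib, will be recorded" at the discontinuation and 60-day visits. The sentence before it has medications recorded at every visit until the final analysis, so an end at 60 days is only one reading. Restaging is done at the trial centre (3.5.2), so the team still sees the patients most able to produce a late response. What is missing is an explicit item for subsequent anticancer treatment.
- **That later responses would be common because some of these patients respond to imatinib or sunitinib.** The same sentence of 1.2.1 describes those responses as often brief and less marked than in KIT- or PDGFRA-mutant disease. Credited-response rates of 5% or 10% of all patients would put the chance of declaring activity at 36% or 63%. The arithmetic is right, but nothing in the protocol points to rates that high.
- **That progression-free survival is wrongly defined.** Section 6.3.6 reads: "Progression-free survival (PFS) is defined as the duration of time from start of treatment to time of progression or death". Following patients to that event whatever they receive next is a legitimate treatment-policy definition, and section 8.2 uses it descriptively. Censoring at new therapy can itself be informative, because patients who switch may differ in prognosis.

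It is also true that any misclassified response, whatever its cause, would turn 0/9 into 1/9. That shows how fragile the rule is; it does not measure how likely this particular error is.

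**Conclusion.** The concern holds for best overall response. The written rules would allow a confirmed decrease caused by a later therapy, or by resection of a target lesion, to be counted as a vandetanib response.

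Its size is modest and uncertain. Under the two milder sets of assumptions the chance of declaring activity at a true 5% rate goes from 9.3% to 11.4% or 12.5%; if 2% of all patients gained a credited response it would be 19%. These are illustrations, not estimates. Because accrual closed at nine patients, the full-design figures have little practical bearing. What matters is whether each response counted at stage 1 arose before any other anticancer treatment. The documents do not show that any patient was affected.

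The point does not extend to progression-free survival. How to treat later therapy there is a choice of estimand, not an error.

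**What to change.** 1. In 6.3.4.3, end the response window at the earlier of progression or the start of any other anticancer treatment, including resection of tumour. Scans after that date do not count toward best response.
2. At contacts that already take place (restaging visits, the off-treatment evaluation and the annual contact in 3.5.3.1), record the date and type of the first subsequent anticancer treatment.
3. Leave 6.3.6 as it stands. Optionally add a sensitivity analysis of progression-free survival censored at the start of new therapy.

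The cost is a sentence of wording and one extra data item. The design, its error rates and the decision rules do not change. The downside is a possibly slightly lower response rate, since a late response to vandetanib that appears after another treatment has started would no longer count. The rule governs analysis, so it can still be applied with accrual closed.
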